3.3.2.1 Loading Dose Period

The Loading Dose Period of the study will occur from Day 1 to Day 29.

- Subjects who have completed Parts A or B of Study 233AS101:
 - Subjects will receive 3 loading doses of tofersen approximately 2 weeks apart (Day 1, Day 15, and Day 29).

- Subjects who have completed Part C of Study 233AS101:
 - Subjects randomized to receive placebo during Study 233AS101 will receive 3 loading doses of tofersen, approximately 2 weeks apart (Day 1, Day 15, and Day 29). The Investigators, study staff (except for an unblinded designated pharmacist/technician), and study subjects will be blinded to the study treatment during the Loading Dose Period.
 - Subjects randomized to receive tofersen during Study 233AS101 will receive 2 loading doses of tofersen, on Days 1 and 29, and 1 dose of placebo on Day 15. The Investigators, study staff (except for an unblinded designated pharmacist/technician), and study subjects will be blinded to the study treatment during the Loading Dose Period.

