3.3.2.2 Maintenance Dose Period

During the maintenance portion of the study, subjects will receive up to 90 doses of tofersen, approximately every 4 weeks, during visits at Weeks 8, 12, 16, and every 4 weeks thereafter until the last subject enrolled has had the opportunity to have their Week 152 Maintenance Dose Visit.

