4.6. Study Treatment Exposure

Summaries for extent of exposure to study treatment will be summarized for the overall safety population by study group.

A frequency distribution for number of doses received per subject will be summarized by study group, and descriptive statistics will be presented for total cumulative dose during 233AS102 in mg. Total cumulative dose will be based on actual dose administered (calculated as volume administered multiplied by dose, and divided by 15mL). For Part A/B subjects the frequency distribution for number of doses received per subject will also be broken down by <100 mg and 100 mg.

A delayed visit or dose will be anything that falls outside of the following protocol-defined windows of +/-3 days

The following summaries will be presented by study group:

- Total number of expected doses across subjects based on actual subject duration of dosing; total number of missed doses and total number of delayed doses (percentages calculated out of total number of expected doses);
- A frequency distribution for number of consecutive missed doses per subject. If a subject has more than one period where doses were missed consecutively, the period with the maximum consecutive missed doses will be used;
- A frequency distribution for overall number of missed doses per subject (i.e. regardless of whether they were consecutive). The mean (SD) will be presented for the mean number of missed doses per subject. Subjects with no missed doses will be included as having 0 missed doses.
- The mean (SD) number of delayed doses per subject will also be summarized. Subjects with no delayed doses will be included as having 0 delayed doses. A delayed dose is based on regular scheduled visits, as dosing cannot be recorded under unscheduled visits.

The summaries described above for missed and delayed doses will be repeated based on doses that are missed or delayed due to COVID-19 impact.

A listing will also be presented to show dosing history for all subjects who missed at least one dose, indicating whether any of the missed doses are related to COVID-19. If any of the doses are due to COVID-19, then the number of impacted doses will be presented.

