4.9.1. Adverse Events

All AEs will be classified using MedDRA version 27.0 or later. All AEs will be listed but only treatment emergent AEs will be summarized, where treatment emergence will be relative to the first dose of study drug. A treatment emergent AE/SAE is defined as any AE/SAE with an onset date and time that is on or after the first dose of study drug or any pre-existing condition that has worsened in severity after the first dose of study drug. In case of missing dates,

- Any AE/SAE with both a missing onset date and resolution date, or any AE/SAE with a missing onset date and a resolution date which is after the first dose of study drug, will be considered treatment emergent.
- If the onset date is available but onset time is missing and the AE onset date is the same as the first dose date the AE will be considered treatment emergent.
- For AEs with a partial start date, the year/month of the event date will be compared to that of the first dose date to determine whether the event is treatment emergent.

The incidence of treatment emergent AEs will be summarized by study group as follows:

- by primary system organ class (SOC) and MedDRA preferred term sorted by decreasing frequency
- by SOC and MedDRA preferred term sorted by alphabetical order
- by MedDRA preferred term
- by SOC

- The most common treatment emergent AEs i.e. occurring in $\geq 5\%$ subjects in any study group will be presented by MedDRA preferred term.
- For Part C subjects only, the most common treatment emergent AEs i.e. occurring in 2 or more subjects in subjects previously on tofersen in 233AS101 compared to subjects who were on placebo will be presented by MedDRA preferred term.
- By maximum CTCAE grade, primary SOC and MedDRA preferred term
- By maximum CTCAE grade and MedDRA preferred term
- AEs with a CTCAE grade ≥ 3 by primary SOC and MedDRA preferred term
- Related AEs by primary SOC and MedDRA preferred term
- SAEs by primary SOC and MedDRA preferred term
- SAEs by MedDRA preferred term
- Related SAEs by primary SOC and MedDRA preferred term
- AEs related to lumbar puncture (as assessed by the investigator) by primary SOC and MedDRA preferred term
- AEs that occurred within 24 hours of dosing by primary SOC and MedDRA preferred term (in case of partial AE start date, if the month and year are available and day is missing, the AE will be included for any dose that occurs in the same month and year as the AE)

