- AEs which led to discontinuation of study drug by primary SOC and MedDRA preferred term
- AEs which led to withdrawal from study by primary SOC and MedDRA preferred term
- AEs which led to drug interrupted by primary SOC and MedDRA preferred term
- AEs which led to hospitalization by primary SOC and MedDRA preferred term (showing number and percentage of subjects with at least one occurrence in that SOC or preferred term, as well as total number of events). Further summaries of hospitalization data are also included later in this section.
- AEs that led to death
- AEs of note (serious neurologic events, falls, CSF laboratory abnormalities) for which preferred terms will be based on a medical review before final analysis and unblinding. This summary will include number and percentage of subjects with at least one event and total number of events. The follow-up adjusted incidence rates based on number of subjects as well as number of events will also be presented in the same table. If any of these are defined based on more than one preferred term, the preferred terms will also be broken down under the overall category.

The sorting order for AE incidence tables, unless otherwise specified, will be by decreasing frequency order of “Total tofersen all doses” column. For the AE summary by primary system organ class and preferred term, subjects will be counted only once within each primary SOC/MedDRA preferred term. For the summary of AEs by maximum CTCAE grade, primary system organ class and preferred term, subjects will be counted only once within each primary SOC/MedDRA preferred term and will only be counted under the maximum CTCAE grade. For the summary of related AEs, if the relationship is missing then this will be summarized as unknown.

For AEs that occurred within 24 hours of dosing, if time of AE is missing and the event occurs on the same day as the day for dosing or the day following dosing, the AE will be counted as occurring within 24 hours of dosing.

An overall summary of AEs will also be presented. A separate table will also be presented to show an overall summary of COVID-19 pandemic related AEs.

Listings of the following events will be produced.

- AEs which led to discontinuation of study drug
- AEs which led to withdrawal from study
- AEs which led to drug interrupted
- AEs related to lumbar puncture
- AEs which led to hospitalization
- SAEs
- AEs

A listing of deaths will be provided if applicable.

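### While 4-weekly dosing continues, the missing-day rule for AEs within 24 hours of dosing is met in almost every month, so it barely discriminates; show these AEs in a separate row

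*SAP*

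**What the plan says.** SAP Section 4.9.1 lists, among the treatment-emergent AE summaries, a table by SOC and preferred term of AEs within 24 hours of dosing. It has two rules for incomplete onset information.

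- **Missing day.** The trigger is "if the month and year are available and day is missing". The action is that "the AE will be included for any dose that occurs in the same month and year as the AE".
- **Missing time only.** The AE counts as within 24 hours "if time of AE is missing and the event occurs on the same day as the day for dosing or the day following dosing". That is two calendar days per dose.

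Nothing else in the section narrows the missing-day rule. It uses neither the resolution date nor the investigator's assessment of relationship to lumbar puncture. No flag, separate count or sensitivity table for these cases is specified.

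The dosing schedule is in SAP Section 3.3.2. Loading doses fall on Days 1, 15 and 29. In maintenance, "subjects will receive up to 90 doses of tofersen, approximately every 4 weeks, during visits at Weeks 8, 12, 16" and so on. SAP Section 4.6 sets the dose window: "A delayed visit or dose will be anything that falls outside of the following protocol-defined windows of +/-3 days". In the AE summary by SOC and preferred term, "subjects will be counted only once within each primary SOC/MedDRA preferred term".

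**The concern.** What this table adds to the overall AE tables is timing. For an AE with no onset day, the rule replaces timing with the question of whether a dose was given at any point in that month. With doses about 28 days apart, the answer is nearly always yes, so the rule sorts hardly anything. It also works in both directions around the dose: an AE that began and was recorded as resolved before that month's dose still satisfies it as written.

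At stake is how the table reads. Loosely dated events in a multi-year ALS population could appear as events in the day after an intrathecal injection, and a reader would have no way to tell from the table how many of its entries rest on a recorded date.

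**Working it through.** The plan gives no figure for this point, so there is nothing to reproduce. The check is calendar counting.

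**Inputs from the documents**
- Loading doses on Days 1, 15 and 29 (SAP 3.3.2.1). I count Day 15 as a dosing day for everyone.
- Maintenance visits from Week 8 every 4 weeks (SAP 3.3.2.2), up to Week 360 (schedule of activities). The listed weeks give (360 − 8)/4 + 1 = 89 visits; one dose more or fewer does not matter here.
- Window of ±3 days (SAP 4.6).
- Comparator: dosing day or the day after, which is the SAP's own missing-time rule.

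**Assumptions**
- Missed doses: 0% to 20%, at random. The documents give no rate.
- Onset day uniformly distributed over the dosing period, that is, unrelated to dosing.

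**Step 1: exact 28-day intervals.** Any 28 consecutive days contain one dose, and every calendar month has at least 28 days. So every month on dosing contains a dose and capture is 100%. In maintenance the comparator is 2/28 = 7.1%.

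**Step 2: windows and missed doses.** With ±3 days, two consecutive doses can be up to 28 + 6 = 34 days apart, so a few months contain none. I simulated 300 schedules per scenario with random start dates and uniform variation within the window.

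| Window | Doses missed | Onset day lies in a month with a dose | Onset on dosing day or day after | Ratio |
|---|---|---|---|---|
| none | 0% | 100% | 7.26% | 13.8 |
| ±3 days | 0% | 98.7% | 7.26% | 13.6 |
| ±3 days | 5% | 94.3% | 6.89% | 13.7 |
| ±3 days | 10% | 89.5% | 6.51% | 13.7 |
| ±3 days | 20% | 80.9% | 5.82% | 13.9 |

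The comparator is 7.26% rather than 7.1% because the loading doses are closer together.

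**Step 3: sensitivity to the onset assumption.** Suppose half of the missing-day AEs truly fell on a dosing day or the day after (an assumption). The true share is 0.5 + 0.5 × 0.0726 = 0.536. With capture of about 0.987, over-inclusion is 0.987/0.536 = 1.8-fold, not 14-fold.

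**Step 4: after the last dose.** For onsets spread over the 28 days after the last dose, 52.6% fall in the same calendar month as that dose. In later months off treatment, capture is zero.

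**Step 5: more than one dose in a month.** With no missed doses, 10% to 11% of months on dosing contain two or more doses (9.7% at exact intervals, 11.0% with windows), so one such AE can be attached to more than one dose.

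**The case against.** The strongest defence is that this is a deliberate, prespecified worst-case convention, consistent with the rest of the plan. In SAP 4.9.1 an AE with neither an onset nor a resolution date is treatment emergent. In SAP 4.12 a confirmed positive antibody sample of undetermined magnitude counts as at least a 2-fold rise. The SAP says these AEs are included in the table; it does not say they are proven to be acute. Related AEs and AEs related to lumbar puncture have their own tables, and all AEs are listed. Restricting the table to known dates would also drop some genuine post-dose events.

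Most of this stands. It is a convention, not an error, and a remedy that simply discarded partial-date AEs would be debatable. It does not answer the narrower point: every treatment-emergent AE is already counted elsewhere, so a worst-case rule protects little here unless the reader can see how much of the count it supplies. The same section already reports missing relationship as unknown rather than as related, and it already uses the resolution date when deciding treatment emergence.

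Three stronger readings are tempting, and the documents do not support them.

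- **The acute tolerability table is inflated about 14-fold.** That ratio applies only to missing-day AEs, and only if they are unrelated to dosing. How many there are is not stated. There may be few: Protocol 15.6.1 requires investigators to determine onset dates, and Protocol 15.3.1 has AEs assessed at every visit and at the telephone contact about 24 hours after each procedure. Because each subject counts once per term, an added AE changes the count only if that subject has no other qualifying event in that term.
- **Nearly every missing-day AE in the study is captured.** This holds only during active dosing. Protocol 10.1 encourages participants who stop treatment to stay in the study, and SAP Section 1 reports a large proportion of discontinuations among Part A and B subjects. AEs with only a year are not covered by the rule.
- **The bias grows with follow-up and differs between the Part A+B and Part C columns.** Follow-up, missed doses and discontinuation may differ, but no figure in the documents shows a difference in this table, and subject-level counting weakens the link to follow-up.

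**Conclusion.** The concern holds as a limited reporting point. During 4-weekly dosing, the rule places about 99% of month-and-year-only AEs in the 24-hour table with no missed doses, and 90% to 94% if 10% to 5% are missed (assumed). About 7% would be expected on a dosing day or the day after if onset were unrelated to dosing. As written it can also include an AE recorded as resolved before that month's dose.

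The consequence is confined to one descriptive secondary table. The primary endpoint, incidence of AEs and SAEs, does not change. The effect on the table's totals cannot be stated without the number of AEs that lack an onset day. The percentages rest on uniform onset within the dosing period, random missed doses and uniform variation within ±3 days. This is a worthwhile improvement, not a defect that threatens a conclusion.

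**What to change.** Amend the 24-hour bullet in SAP 4.9.1 so that the table shows three things:

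1. AEs with a known onset date that qualify, keeping the existing missing-time rule.
2. A separate 'timing unknown' row for AEs with a missing day in a month with a dose, leaving out any AE whose recorded resolution date precedes every dose given in that month.
3. The combined total of the two, labelled as the worst case.

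This costs one sentence in the SAP and one extra row, plus the combined total. The downside is that the known-date line is less conservative than the current count. The worst-case total preserves that count, apart from AEs already resolved before the dose. If few AEs lack an onset day, the row will be nearly empty and the reader will know that too.

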QTc	interval between the start of the QRS complex and the end of the T wave, corrected for heart rate
QTcF	QTc interval using Fridericia's formula
RBC	red blood cell (count)
RNA	ribonucleic acid
RR	inter-beat
SAE	serious adverse event
SAP	statistical analysis plan
SAS	statistical analysis system
SD	standard deviation
SDTM	standard data tabulation model
SE	standard error
[REDACTED]	[REDACTED]
SOC	system organ class
SOD	superoxide dismutase 1
SVC	slow vital capacity
ULN	upper limit of normal
WBC	white blood cell (count)
WHO	World Health Organization
[REDACTED]	[REDACTED]
[REDACTED]	[REDACTED]

1. Introduction

Study 233AS102 is an extension study of 233AS101 to assess the long-term safety, tolerability, pharmacokinetics, pharmacodynamics, and efficacy of BIIB067 administered to previously treated adults with ALS caused by SOD1 mutation, who have completed Parts A, B, or C of Study 233AS101.

Study 233AS101 is a randomized, double-blind, placebo-controlled, 3-part study to examine the efficacy, safety, tolerability, pharmacokinetics (PK), and pharmacodynamics (PD) of BIIB067, administered by intrathecal bolus injection in subjects with ALS and a confirmed SOD1 mutation.

This statistical analysis plan (SAP) is prepared to describe the final analysis for the closeout clinical study report for 233AS102; separate SAPs exist for 233AS101 Parts A and B, 233AS101 Part C, and integrated analyses across the studies. Prior versions of the SAP for 233AS102 (Versions 1.0 to 3.0) were generated for the purpose of interim analyses based on interim data cuts for the study.

BIIB067 will be referred to as tofersen throughout the rest of the statistical analysis plan.

There are limitations for subjects who enrolled from 233AS101 Parts A and B which impact the interpretability of these subjects in 233AS102:

- Subjects who completed Parts A or B of 233AS101 had a significant washout period ranging from 16 weeks to over 2 years from their last dose of study treatment in 233AS101 to their first dose in 233AS102.
- Dosing paradigms varied substantially across subjects as dose levels in 233AS102 were increased over time as additional doses were deemed to have an acceptable safety profile in 233AS101.
- Many subjects had meaningful disease progression during the washout and exposure to lower doses resulting in a large proportion of discontinuations across studies

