Study drug compliance percentage up to the last dose of study drug received will be defined as the number of doses actually received divided by the number of doses that the subject is expected to receive during the study period and will be summarized by descriptive statistics. For subjects who withdrew from study early, the number of expected doses is the planned number of doses before the time of withdrawal.

Study drug administration data will be listed which will include lot numbers, dose received, cumulative number of doses and cumulative dose. A listing of dosing errors will also be provided

i.e. where either the incorrect dose was administered as specified in protocol deviation log and kit description from IRT system. Actual dose will be calculated as volume administered multiplied by dose and divided by 15mL. The nominal dose will also be presented.

Time on study will be summarized descriptively by study group. Overall time on study will be calculated as last date on study at time of cutoff – first dose date + 1 in days. Last date on study is defined as the date of the latest visit or evaluation or telephone contact, or time of death from all available data for a given subject. The durations will also be categorized and summarized using 12-week intervals the following categories: ≤12 weeks, >12 weeks to 24 weeks, >24 weeks to 36 weeks, >36 weeks to 48 weeks, >48 weeks to 60 weeks, >60 weeks to 72 weeks, >72 weeks to 84 weeks, and so on.

A summary of time to treatment discontinuation will be provided for those subjects who discontinued study drug, calculated as last dose date – first dose date +1.

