An additional table for hospitalizations will present the number and percentage of subjects in each treatment group with at least one hospitalization, the number of hospitalizations per subject, total number of hospitalization and a descriptive summary for the total cumulative duration of hospitalizations per subject.

Pre-treatment SAEs i.e. those that occurred between screening and first dose are not considered treatment emergent and so will be summarized separately if there is a sufficient number. Pre-treatment AEs should not be collected unless classed as serious. All SAEs will be listed, with an indicator for pre-treatment SAEs. Only treatment emergent AEs will be summarized, unless otherwise specified.

A separate summary will be presented for each confirmed COVID-19 AE and suspected COVID-19 AE. These will be identified as AEs that are recorded with an entry of '(Confirmed)' and '(Suspected)'. As per the guidance, confirmed cases are those confirmed via a diagnostic test and suspected cases are those diagnosed based on typical symptoms, travel/contact history. A listing will also be provided.

Incidence rate tables

Incidence and incidence rate will be provided in incidence rate tables and will be summarized by primary SOC and MedDRA preferred term by study group. Two different kinds of incidence rate tables will be provided. Definitions are provided below:

- 1) Follow-up adjusted incidence rate – defined as the number of subjects who experienced an event divided by the total of entire follow-up time among the subjects in the analysis population. The entire follow-up time for subject is defined as the time from the first dose until the last day (the earliest date of last study day and interim cutoff date) on study. Each subject will be counted only once within each category. A similar table will also be based on total number of events divided by the total of entire follow-up time among the subjects in the

analysis population. This may count a subject more than once within each category of they experienced an event more than once.

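### The hospitalisation tables in SAP 4.9.1 give counts and days with no person-time rate, so differences between study groups may be confounded by time on study

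*SAP*

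**What the plan says.** SAP 4.9.1 has two hospitalisation outputs.

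- A table of "AEs which led to hospitalization by primary SOC and MedDRA preferred term". For each class or term it counts the people affected, with a percentage, and the events.
- A separate hospitalisation table: subjects with at least one admission (number and percentage), then "the number of hospitalizations per subject, total number of hospitalization and a descriptive summary for the total cumulative duration of hospitalizations per subject".

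Person-time rates appear elsewhere in the same section. For AEs of note (serious neurologic events, falls, CSF laboratory abnormalities) the SAP says: "The follow-up adjusted incidence rates based on number of subjects as well as number of events will also be presented in the same table". For AEs by system organ class and preferred term, "Two different kinds of incidence rate tables will be provided": a follow-up adjusted rate and an exposure-adjusted rate. The first also has an event-based form: "A similar table will also be based on total number of events divided by the total of entire follow-up time among the subjects". Its denominator is time from first dose to the last day on study.

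SAP 4.6 adds, in a different table, "Time on study will be summarized descriptively by study group". Protocol 16.6.2.1 treats person-year rates for AEs as optional once long follow-up has built up.

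**The concern.** Every quantity in the two hospitalisation tables grows with time at risk: the percentage ever admitted, the number of admissions and the days in hospital. Follow-up is unequal by design, because everyone stops on a rule tied to the last participant enrolled. It is unequal in practice too, because people die or withdraw.

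The study groups in SAP Table 6 are set side by side. At the same underlying rate, a group followed longer would show more admissions and more days. A group that loses participants early would show fewer, which in a fatal disease is the wrong signal. The primary objective is long-term safety, and SAP section 1 limits the standalone report to safety and exposure, so readers are likely to compare these columns.

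**Working it through.** **1. Is a hospitalisation rate planned anywhere?** Both hospitalisation tables list only subjects, events, counts and days. The rate tables are built by system organ class and preferred term. Hospitalisation is an outcome of an event, not a preferred term, so it has no row there. The AEs-of-note categories do not include it. No rate for hospital days is defined at all.

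**2. How far can follow-up differ?**

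- Protocol 7.2: screening 4 + treatment 360 + follow-up 4 = 368 weeks, which reproduces the stated maximum participation.
- From first dose: 360 + 4 = 364 weeks; 364 × 7/365.25 = 6.98 years. SAP Table 3 agrees: the Week 364 target day is 364 × 7 + 1 = 2549.
- Shortest planned follow-up for a completer (Protocol 7.4 and 7.2.3): 152 + 4 = 156 weeks, or 2.99 years.
- Ratio between completers at the extremes: 364/156 = 2.33.
- Early leavers: the first time-on-study category in SAP 4.6 is 12 weeks or less; 364/12 = 30.3.

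**3. What does that span do at one constant rate?** The documents give no hospitalisation rate, so the rates r below are assumptions. The expected count is r × T, and the chance of at least one admission is 1 − exp(−r × T).

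| Assumed r per person-year | Mean count, 156 weeks | Mean count, 364 weeks | At least one, 156 weeks | At least one, 364 weeks |
|---|---|---|---|---|
| 0.2 | 0.60 | 1.40 | 45% | 75% |
| 0.5 | 1.49 | 3.49 | 78% | 97% |
| 1.0 | 2.99 | 6.98 | 95% | 99.9% |

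These rows compare two individuals at the ends of the planned range. They do not compare two study groups.

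**4. How much of the spread between subjects is time on study?** With no difference in risk, its share of the variance in counts is r × Var(T) / (E[T] + r × Var(T)). I assume T is uniform.

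| Assumed range of T | r = 0.2 | r = 0.5 | r = 1.0 |
|---|---|---|---|
| 156 to 364 weeks | 5% | 12% | 21% |
| 12 to 364 weeks | 17% | 34% | 51% |

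**5. What happens between columns?** At equal rates, the ratio of counts per subject equals the ratio of mean follow-up. The documents do not give mean follow-up by group, so this ratio cannot be computed. An invented example with 50 subjects per column shows what the planned table would hide.

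| Column | Mean follow-up | Person-years | Admissions | Per subject | Per 100 person-years |
|---|---|---|---|---|---|
| A | 2.0 years | 100 | 50 | 1.00 | 50/100 = 50 |
| B | 3.5 years | 175 | 87.5 | 1.75 | 87.5/175 = 50 |
| C | 3.5 years | 175 | 50 | 1.00 | 50/175 = 28.6 |

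A and B have the same rate but look different per subject. A and C look the same per subject but have different rates.

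**6. Which columns are exposed?** The two Part C groups share an entry process and a stopping rule, so their follow-up would differ mainly through unequal withdrawal or death. Parts A+B against Part C is the clearer risk. Part C began entering only under protocol version 4 (SAP 2.3), so Parts A/B participants could enter earlier. But SAP section 1 reports "a large proportion of discontinuations across studies" for them. These pull in opposite directions.

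**The case against.** The strongest reply is that the tables are descriptive and supplementary. Hospitalisation is not an endpoint, and no test or sample size rests on it. Inpatient hospitalisation is an SAE criterion (Protocol 15.1.2), so the underlying events should enter the planned AE rate tables. Time on study is summarised for the same groups, so a reader can multiply group size by mean follow-up and divide it into total hospitalisations. Other subset tables, such as SAEs or AEs leading to discontinuation, also specify incidence only. And a pooled rate over up to seven years of a progressive disease mixes disease stage with survivor selection, so it is not automatically a fair comparison.

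Most of this stands, and it limits the importance of the point. It does not close the gap. A crude admission rate worked out by hand is not a planned analysis. Hospital days per person-year could only be approximated, since the SAP does not say whether subjects never admitted count as zero days in the duration summary. The SAP already puts rates in the same table for AEs of note and gives no reason to treat hospitalisation differently.

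A reader might infer that the columns mainly reflect time on study, or that follow-up differs strongly between all of them. The documents do not support either. No group mean follow-up is given, the 2.33-fold span is between individuals, and the variance share passes one half only in the widest range at the highest assumed rate. Nor does it follow that the table can say nothing about long-term safety: the counts are valid descriptions of what happened.

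**Conclusion.** The point holds as a cheap improvement. No person-time rate is planned for hospitalisations or hospital days, while follow-up from first dose can run from weeks to 364 weeks (156 to 364 for planned completers). Differences between study groups, chiefly Parts A+B against Part C, may be confounded by time on study, in a direction that cannot be predicted from the documents.

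The size of any distortion is unknown. The figures above rest on assumed constant rates of 0.2 to 1.0 per person-year, uniform follow-up and invented group means. They show that the effect can be material, not that it will be.

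**What to change.** In the separate hospitalisation table of SAP 4.9.1 add two rows by study group:

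- total hospitalisations divided by total person-years;
- total hospital days divided by total person-years, with subjects never admitted contributing zero days.

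Use as denominator the entire follow-up time that 4.9.1 already defines for the follow-up adjusted AE rate, summed over the safety population. Report both rates beside the raw counts whenever the CSR compares groups. Keep the counts and percentages as they are.

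The cost is two rows, with a denominator that the SAP already defines. The rates still average over disease stage and over who survives to be followed, so they remain descriptive and the CSR should say so.
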